8.7 Reporting of technical complaints

Any technical complaint related to the trial products provided by ALK (IMP, asthma and rhinoconjunctivitis rescue medication and SPT) must be reported to ALK. The information must be accompanied by samples or a picture of the item.

9 Treatment

9.1 Posology and method of administration

The IMP-tablet should be taken with dry fingers from the blister unit immediately after opening the blister and placed under the tongue, where it will disperse. Swallowing should be avoided for approximately 1 minute.

Food and beverages should not be taken for 5 minutes after intake of IMP. The daily dose of IMP is 1 SLIT-tablet, which should preferably be taken in the morning.

9.2 Precautions in relation to first dosing

First intake of IMP should be at the clinic with a minimum of 30 minutes observation period after the intake. For the recording of onset and duration of solicited AEs that occur on Day 1 (visit 3), the subject should remain in the clinic for 60 minutes after IMP intake.

Prior to IMP intake an oropharyngeal examination should be performed. This should be repeated 60 minutes after IMP intake.

For subjects with severe oral inflammation (e.g. oral lichen planus, mouth ulcers or thrush), oral wounds or following oral surgery, including dental extraction, or following tooth loss, initiation of IMP treatment should be postponed until the oral cavity has healed.

For subjects with symptoms of, or in treatment for, upper respiratory tract infection, acute sinusitis, acute otitis media or other relevant infections, initiation of IMP treatment should be postponed until the condition has improved.

For subjects with a severe asthma exacerbation within the last 30 days prior to randomisation treatment initiation should be postponed by minimum 30 days from the time of the severe asthma exacerbation (start of OCS treatment or first day of hospitalisation). The treatment initiation can be postponed maximum 3 times.

Only subjects meeting all inclusion criteria listed in Section 4.1 and none of the exclusion criteria in Section 4.2 are considered eligible for randomisation and first dosing.

9.3 Rescue medication for severe allergic reactions

In countries where it is a regulatory requirement, the subject/parent/caregiver will be provided with two adrenaline/epinephrine auto-injectors at the randomisation visit (visit 2). The

investigator will instruct the subject/parent/caregiver on how to use the adrenaline/epinephrine auto-injectors and to have it available when tablet is administered.

Adrenaline/epinephrine auto-injectors are intended for immediate self-administration for an anaphylactic reaction, including symptoms/signs of upper airway obstruction. Anaphylaxis is likely when multiple organ systems are adversely affected following exposure to an allergen. A list of symptoms that may be present during anaphylaxis include flushing, apprehension, syncope, tachycardia, thread or unobtainable pulse associated with a fall in BP, vomiting, diarrhea and abdominal cramps, wheezing, dyspnea due to laryngeal spasm, lower airway obstruction, pruritus, rashes (such as urticaria), or angioedema. Self-injectable adrenaline/epinephrine should be administered promptly when significant respiratory and/or cardiovascular symptoms accompany an allergic reaction.

Subjects experiencing symptoms of an anaphylactic reaction without access to an adrenaline/epinephrine auto-injector must immediately call the local emergency number.

At visit 2, the subject/parent/caregiver will also be provided with educational information regarding symptoms of anaphylaxis and treatment, including a written Local and Systemic Allergic Reaction Emergency Plan (Epstein et al. 2017). The investigator will provide written instructions and explain to the subject/parent/caregiver, when to administer the adrenaline/epinephrine auto-injectors. The investigator will complete a Local and Systemic Allergic Reaction Emergency Plan for each subject, provide a copy to the subject/parent/caregiver, and keep a copy for the site's records (Section 11.20).

In the event that the adrenaline/epinephrine auto-injector is used, the subject/parent/caregiver must immediately call the local emergency number. The subject must inform the investigator and an unscheduled visit should be arranged to further evaluate the subject. The investigator must report the event to the Sponsor within 24 hours of first becoming aware of the use of an adrenaline/epinephrine auto-injector. The symptoms and/or circumstances that triggered the use of the adrenaline/epinephrine auto-injector must be clearly recorded on the eCRF.

At each visit following the dispensing, the investigator or designee will verify that the subject has adrenaline/epinephrine auto-injectors and will review instructions for use. Unused adrenaline/epinephrine auto-injectors will be collected at visit 11.

9.4 Temporary interruption and discontinuation of treatment

Treatment may be discontinued for up to 7 days for the following reasons:

- In case of oral surgery, including dental extraction and shedding of a deciduous tooth, to allow healing of the oral cavity
- Inflammatory conditions in the oral cavity
- Upper airway viral infection
- Other reasons if deemed necessary by the investigator

Interruptions should be kept to a minimum. If IMP is interrupted for more than 7 days in a row, the subject should contact the investigator before restarting the treatment.

If IMP treatment is permanently discontinued, the subject may be discontinued from the trial.

ALK should be notified in case of IMP discontinuation due to an AE.

In case of a severe asthma exacerbation, IMP treatment should be discontinued temporarily while the subject is treated with OCS or while hospitalised. If the interruption is lasting for more than 7 days, the subject should contact the investigator before restarting the treatment.

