Period 2 is the baseline period of 3 weeks following screening. For cohort 1, the baseline period is during Q1 - Q2 2018. For cohort 2, the baseline period is during Q4 2018 - Q2 2019. For cohort 3, the baseline period is during Q4 2019 - Q2 2020. For cohort 4, the baseline period will occur during Q4 2021 – Q2 2022. During the baseline period, eligible subjects or their parent/caregiver will fill in their asthma and rhinoconjunctivitis symptoms and medication use in an eDiary. Subjects will continue with their regular asthma background treatment. The subjects' regular asthma rescue mediation and rhinoconjunctivitis rescue medication must be replaced with the rescue medication provided by ALK at visit 2 with the exception of additional sponsor provided ICS, which is optional.

Period 3 is the treatment initiation and maintenance period to allow the treatment with the HDM SLIT-tablet to take effect. It starts at randomisation and lasts for at least 4 months. The period ends on 1 September 2018 for cohort 1, on 1 September 2019 for cohort 2, on 1 September 2020 for cohort 3 and on 1 September 2022 for cohort 4.

During the first 28 days of period 3, prespecified symptoms⁴⁰ occurring after IMP intake will be recorded by the subject/parent/caregiver in the eDiary. The reported symptoms will be evaluated by investigator and reported in the eCRF as solicited AEs.

Period 4 is the efficacy assessment period. Period 4 lasts until the end of trial or discontinuation from the IMP⁴¹ and during this period the rate of clinically relevant asthma exacerbations will be

⁴⁰ AEs identified by the World Allergy Organization (WAO) as local side effects of SLIT (Passalacqua et al. 2013).

⁴¹ Subjects will be discontinued from the IMP treatment after 2 severe asthma exacerbations in 12 consecutive months or 1 hospitalisation due to asthma requiring treatment with systemic corticoteroids.

evaluated from 1 September 2018 to 30 April 2020 (cohort 1), 1 September 2019 to 30 April 2021 (cohort 2), 1 September 2020 to 30 April 2022 (cohort 3) and 1 September 2022 to 30 April 2024 (cohort 4).

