5.1 Discontinuation from IMP treatment

Subjects must be discontinued from IMP treatment and should continue in the trial for safety assessments only under the following circumstances:

- If the subject experiences 2 severe asthma exacerbations within a 12 consecutive months period
- If the subject is hospitalised due to asthma requiring treatment with systemic corticosteroids
- The subject experiences severe or persistent symptoms of oesophagitis
- If the subject becomes pregnant
- If, in the investigator's opinion, continuation with IMP treatment would be detrimental to the subject's well-being

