11.16 Asthma exacerbation assessment

An Asthma Action Plan (Section 11.19) will be given to the subjects and parents/caregivers to provide guidance to effectively manage the subject's symptoms, as recommended by clinical practice guidelines. Subjects will be trained in their Asthma Action Plan by the investigator or designee.

According to the Asthma Action Plan subjects must contact the investigator when asthma symptoms increase or in cases with reduction in lung function. The investigator or designee will fill in the appropriate treatment for the subjects in the Asthma Action Plan.

Subjects will continue with a constant dose of low dose ICS plus LABA or medium/high dose ICS with or without LABA throughout the trial.

If a subject presents with worsening of asthma symptoms, investigator or designee should always evaluate if the subject requires treatment at emergency room. If emergency room visit is not required initial treatment can be either:

- Doubling of ICS dose compared to background treatment for 2 weeks, or
- Systemic corticosteroids for treatment of asthma symptoms for at least 3 days

For the doubling of ICS dose a separate inhaler with ICS will be provided by ALK as part of the asthma rescue medication. Subjects may also double their ICS dose by using their background medication. Subjects that receive high dose ICS as background treatment are not allowed to double the dose of ICS. Please note that local regulations and SmPCs or USPI must be followed. In case of an asthma exacerbation requiring systemic corticosteroids, the subjects should be treated with OCS in the form of Prednisolone/Prednisone tablets. Dosing regimen should follow recommendations by GINA guideline (GINA Executive Committee 2017), NIH guidelines (National Heart Lung and Blood Institute 2007) or national guidelines (Reddel et al. 2009). See Section 8.3.

The use of LTRA is permitted for continued use only but will not be provided by ALK.

If a subject has 2 severe asthma exacerbations within 12 consecutive months or is hospitalised due to asthma requiring treatment with systemic corticosteroids the subject must be discontinued from the IMP treatment.

Each severe asthma exacerbation must be separated by >7 days from the discontinuation of OCS to be considered an individual event (Lanier et al. 2009).

Each clinically relevant asthma exacerbation must be separated by >7 days from the discontinuation of additional ICS or OCS to be considered an individual event.

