#### AE Start $data_{event=i} - AE$ Stop $date_{event=i-1} > 7$ days

If there are 7 days or less between 2 or more successive clinically relevant asthma exacerbations, the asthma exacerbations will be considered 1 single event starting with the start date of the first asthma exacerbation and ending with the stop date of the last asthma exacerbation. If either clinically relevant asthma exacerbation fulfils 1 of the criteria for being a severe asthma exacerbation the entire event is considered to fulfil that criterion.

#### 7.1.1.2 Annualised rate of clinically relevant asthma exacerbations in period 4

The efficacy assessment period (period 4) begins on the 1st of September for all subjects and lasts until the end of trial visit or discontinuation from IMP. The annualised rate of clinically relevant asthma exacerbations is calculated for each subject as the number of observed clinically relevant asthma exacerbations divided by the time in years in period 4. For the statistical analyses of clinically relevant asthma exacerbations based on a negative binomial regression model the number of clinically relevant asthma exacerbations will be the response variable and the log10 transformed time in years in period 4 will be the corresponding offset.

For each subject, the number of clinically relevant asthma exacerbations is the sum of all clinically relevant asthma exacerbations with a start date in period 4 while the subject is still on IMP. The time in period 4 is calculated as the time in years from start in period 4 until last day of IMP intake, i.e.:

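### Protocol 9.4 lets IMP restart after a hospitalised or repeat severe exacerbation, while 5.1, 11.16, footnote 41 and the synopsis require it to be stopped

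*Protocol*

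**What the plan says.** **Temporary interruption.** Protocol 9.4: "In case of a severe asthma exacerbation, IMP treatment should be discontinued temporarily while the subject is treated with OCS or while hospitalised". It continues: "If the interruption is lasting for more than 7 days, the subject should contact the investigator before restarting the treatment". It neither excepts any severe exacerbation nor points to 5.1.

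**Mandatory stop.** Protocol 5.1: "Subjects must be discontinued from IMP treatment and should continue in the trial for safety assessments only under the following circumstances". One listed circumstance is "If the subject is hospitalised due to asthma requiring treatment with systemic corticosteroids"; another is two severe exacerbations within 12 consecutive months. Section 11.16 repeats the rule: the subject has two such exacerbations or "is hospitalised due to asthma requiring treatment with systemic corticosteroids the subject must be discontinued from the IMP treatment". Footnote 41 in 3.1 repeats it as well: "Subjects will be discontinued from the IMP treatment after 2 severe asthma exacerbations in 12 consecutive months or 1 hospitalisation due to asthma". The synopsis, under subject safety precautions, says the same.

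**Link to the analysis.** SAP 7.1.1.2: "The time in period 4 is calculated as the time in years from start in period 4 until last day of IMP intake". Only exacerbations that start in period 4 while the subject is on IMP are counted (Protocol 15.8, SAP 7.1.1.2). Under the SAP's secondary estimand (1.1.9.6), a subject who discontinues treatment during period 4 contributes no period 4 data.

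**The concern.** The stopping rule is one of the protocol's stated protections for children at risk of severe exacerbations (Protocol 1.4). A site that opens the section on treatment interruptions finds an instruction which, followed literally for a child hospitalised for asthma, breaches 5.1.

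The rule also decides data. IMP discontinuation closes the child's counted time and events in the primary analysis and removes the child from the secondary estimand. It can also put the child out of the per-protocol set, which needs at least 6 months of period 4 assessment. A restart followed by completion keeps the child in the first two and can do so in the third. In sensitivity analysis 2, a placebo child who restarts and completes can serve as a donor for imputation; one who stops cannot. The children concerned are among the most severely affected in the trial.

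**Working it through.** **1. Where the rules meet.** All three criteria for a severe exacerbation (table of definitions) involve systemic corticosteroids.

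| Situation | 9.4 | 5.1, 11.16, footnote 41, synopsis | Conflict |
|---|---|---|---|
| First severe exacerbation, treated out of hospital | temporary | no stop triggered | no |
| Hospitalised for asthma, systemic corticosteroids needed | temporary | stop | yes |
| Second severe exacerbation within 12 months | temporary | stop | yes |
| Severe exacerbation (at least 3 days of systemic corticosteroids) in a child admitted for another cause | temporary | hospitalisation criterion not met | no, unless it is the second in 12 months |

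**2. One child.** Full period 4 is 608 days (Protocol 15.2.1). Suppose the only event is a hospitalisation on day 100.

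- Stop: about 100/365 = 0.27 years and 1 event, an individual rate of 365/100 = 3.65 per year.
- Restart and complete: 608/365 = 1.67 years and the same event plus any later ones. With none, the rate is 365/608 = 0.60 per year.
- Added time: (608 − 100)/365 = 1.39 years. Expected later events at the planning rate: 1.4 × 1.39 = 1.95 on placebo and, with a rate ratio of 0.7, 0.98 × 1.39 = 1.36 on active.

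The added time is 1.50 years for a stop on day 60, 0.84 on day 300 and 0.43 on day 450. The hospitalisation itself counts either way, because it starts on IMP.

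**3. The plan's own sample size.** Protocol 15.1 gives N = {(z₁₋β + z₁₋α/2)/log(μ₁/μ₂)}² × {(μ₁+μ₂)/(μ₁μ₂) + 2k}. With μ₁ = (0.64/24) × 86 = 2.293, μ₂ = 0.7 × 2.293 = 1.605, k = 0.7, 90% power and two-sided 5%, N = 203.1 per arm against 202 stated. The figure reproduces and is not in dispute.

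**4. Trial-level power.** The documents give no hospitalisation frequency, so the shares below are assumptions. Take 300 × 0.7 = 210 contributing subjects per arm. If a share h stops halfway through period 4, mean time is 608 × (1 − h/2) days and μ₁ = 1.4 × that time/365. Power = Φ{√[N/((μ₁+μ₂)/(μ₁μ₂) + 2k)] × log(μ₁/μ₂) − 1.96}.

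| h | Mean days | Power |
|---|---|---|
| 0 | 608.0 | 91.1% |
| 2% | 601.9 | 91.0% |
| 5% | 592.8 | 90.8% |
| 10% | 577.6 | 90.5% |
| 20% | 547.2 | 89.8% |

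**5. Trial-level rate ratio.** A simulation used gamma frailty with k = 0.7, 1.4 events per year on placebo, a true ratio of 0.70, 400,000 children per arm, and a stop at the first hospitalisation. The hospitalised share of exacerbations is again assumed.

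| Share of exacerbations hospitalised | Stopped, placebo / active | Events per placebo child, no stop → stop | Crude ratio under stop |
|---|---|---|---|
| 2% | 4.5% / 3.2% | 2.33 → 2.24 | 0.970/1.378 = 0.70 |
| 5% | 10.6% / 7.6% | 2.33 → 2.12 | 0.951/1.348 = 0.71 |
| 10% | 19.5% / 14.2% | 2.33 → 1.95 | 0.927/1.303 = 0.71 |

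The simulation covers the hospitalisation criterion only, applies one rule to everyone, and uses crude rates rather than the fitted model.

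**The case against.** The strongest reply is that no real choice was open to sites. The stop is worded as *must* or *will* in four places, against one *should* in 9.4, and 9.4 can be read as an acute hold after which 5.1 is applied. Much of this stands: the weight of the text favours the mandatory wording, and nothing in the documents shows that sites acted differently. A reader might infer inconsistent practice between sites or countries; the documents do not support that. But 9.4 nowhere says that it is only a hold, and its restart sentence is not limited to children treated out of hospital.

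Oversight is also in place. Exacerbations, SAEs and events of special interest must be reported within 24 hours (11.16, 12.3), and deviations must be documented (16.4). That makes restarts traceable; it does not reconcile the text.

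A reader might also conclude that the hospital clause of 9.4 can never apply without breaching 5.1. That goes too far, as the fourth row of the first table shows. Nor does 5.1 use the word permanent; that is inferred from the requirement to discontinue and to continue for safety assessments only.

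The sixfold gap in the day-100 example (608/100 = 6.1) might be taken as the size of a bias. It is one hypothetical child's rate with no later event. The primary model analyses counts with log time as an offset, which adjusts for shorter time at risk. Sites and sponsor are blinded, so no mechanism for applying the rules differently by arm is identified. Stops would still be more frequent on placebo if treatment works, but in the simulation this moves the ratio only from 0.70 to 0.71. A stop also does not lose the child everywhere: in sensitivity analysis 2, a subject who stops IMP but completes the trial contributes all observations.

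Finally, SAP 1.1.9.3 reports that only 3 subjects stopped treatment without leaving the trial at that time. This settles nothing: few triggering events, withdrawals or restarts would all produce it.

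**Conclusion.** Wrong as written, within limits. Section 9.4 contradicts 5.1, 11.16, footnote 41 and the synopsis in two situations: a hospitalisation due to asthma needing systemic corticosteroids, and a second severe exacerbation within 12 months. For such a child the rule followed changes counted time by about 0.43 to 1.50 years (stop between day 450 and day 60), decides whether later events count, and decides inclusion in the secondary estimand.

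At trial level, the illustrations give a loss of about one percentage point of power with 20% stopping halfway, and a crude ratio of 0.71 against 0.70 with 10% of exacerbations hospitalised. These rest on assumed frequencies, the planning values (1.4 per year, k = 0.7, ratio 0.7) and uniform application. They do not bound the effect if the rules were applied unevenly.

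A reader might infer that hospitalised children should all be truncated at the event in the analysis. The documents do not support that. The SAP already applies one cut-off, last IMP intake, and the primary estimand runs to end of trial or treatment discontinuation. Truncating children who really resumed IMP would discard on-treatment time selectively, on a component of the primary endpoint.

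**What to change.** - **Text.** Reconcile 9.4 with 5.1, 11.16, footnote 41 and the synopsis so that one rule applies to each of the two situations, and add a cross-reference in 9.4. Which rule applies is for the sponsor's clinical team. The SAP gives 10 August 2022 as the end of trial, so this now mainly serves the record and the trial report.
- **Blinded listing before unblinding.** From existing eCRF data, list subjects who met either asthma criterion in 5.1, flag those who restarted IMP, and report them as protocol deviations where applicable. Draw on SAE hospitalisations as well as the exacerbation criteria on the AE form: the 5.1 trigger has no minimum stay, whereas the exacerbation criterion requires more than 12 hours.
- **Analysis.** Keep the period 4 cut-off at last IMP intake unchanged.

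The cost is a short edit to 9.4 and one listing. No visits, patients or new data are needed.

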9.5 IMP compliance

Subjects must be instructed to bring all residual and unused IMPs and all empty packaging to the site at every visit. Compliance will be assessed at each visit by SLIT-tablets counts. If IMP compliance is less than 80% or more than 100%, the investigator should discuss the reason and educate the subject to comply with the protocol.

The site staff should in cooperation with the subject aim at keeping the IMP compliance above 80%.

9.6 Post-trial treatment

After the end of the trial, the investigator must advise trial subjects on access to appropriate and available treatment. Such treatment will not be sponsored by ALK.

10 Visit schedule

In Table 6, the procedures that should be performed at each visit is described. The procedures are listed in the chronological order in which they should preferably be performed:

Visit ID	Procedures to be performed at the visit
Visit 1 (screening)	 Obtain written informed consent for the trial, storage of serum samples in the ALK Research Biobank, and for pharmacogenetic testing, before any other trial procedures are performed Obtain demographic data (sex, date of birth, race, ethnic origin) Record medical history Rhinoconjunctivitis and asthma medication history Evaluate previous asthma exacerbations Assess eosinophilic oesophagitis Record use of relevant concomitant medication Height and weight Measure vital signs Perform physical examination Measure FEV1 and calculate the % of predicted FEV1 after 6 hours of SABA washout Collect urine for pregnancy test if applicable (No data are available for SPT in pregnant subjects, therefore perform the urine pregnancy test before SPT) Perform SPT and evaluate results⁵⁴ (to be performed at visit 2, if wash-out of concomitant medication is required) Assess compliance with inclusion and exclusion criteria Collect blood and urine sample for safety laboratory assessments

Table 6Visit schedule

⁵⁴ If medication that could interfere with the skin prick test, according to Table 9, has not been washed out and the positive control is <3 mm for subjects in Europe and <5 mm for subjects in North America, the skin prick test must be repeated after the interfering medication has been washed out.

Visit ID	Procedures to be performed at the visit
	 Collect blood sample for specific IgE against D. pteronyssinus, D farinae, Cladosporium herbarum and Blattella germanica Assess AEs Schedule date for visit 2
TC1	 Inform subjects of continued participation in trial depending on the blood sample for specific IgE against D. pteronyssinus and D. farinae Assess AEs occurring since the last visit Evaluate asthma exacerbations occurring since the last visit Record changes to concomitant medication
Visit 2 (baseline)	 Assess AEs occurring since the last visit Evaluate asthma exacerbations occurring since the last visit Assess eosinophilic oesophagitis Record changes to concomitant medication Re-assess compliance with inclusion and exclusion criteria Perform oropharyngeal examination Measure height and weight Measure vital signs Measure FEV1 and calculate the % of predicted FEV1 after 6 hours of SABA washout Collect urine for pregnancy test (if applicable) SPT, if not possible at visit 1 due to necessary wash-out of concomitant medication Evaluate inhalation technique Instruct the subject and/or parent/caregiver on how to use the asthma and rhinoconjunctivitis rescue medication Dispense asthma and rhinoconjunctivitis rescue medication Show Trial Video Issue and instruct the subject and/or their parent/caregiver in the use of the Asthma Action Plan. Dispense Peak Expiratory Flow (PEF) Meter Instruct the subject and/or their parent/caregiver in the use of rescue medication for severe allergic reaction (adrenaline/epinephrine auto-injector) in countries where this is a regulatory requirement Issue and instruct the subject and/or their parent/caregiver in the use of the Local and Systemic Allergic Reaction Emergency Plan Issue and instruct the subject and/or their parent/caregiver in the use of the eDiary for the next 21 days Activate the eDiary Schedule date for visit 3
TC2	 Assess AEs occurring since the last visit Evaluate asthma exacerbations occurring since the last visit Record changes to concomitant medication

Visit ID	Procedures to be performed at the visit
Visit 3 (Randomisation)	 Assess AEs occurring since the last visit Evaluate asthma exacerbations occurring since the last visit⁵⁵ Assess eosinophilic oesophagitis Record changes to concomitant medication Check eDiary compliance Re-assess compliance with inclusion and exclusion criteria Randomise the subject Measure height and weight. If necessary adjust Asthma Action Plan Measure vital signs Measure FEV₁ and calculate the % of predicted FEV₁ after 6 hours of SABA washout Collect urine for pregnancy test (if applicable) Dispense asthma and rhinoconjunctivitis rescue medication as needed Instruct in the use of asthma and rhinoconjunctivitis rescue medication Collect used rescue medication for severe allergic reaction Collect used rescue medication if new rescue medication is dispensed Evaluate ACQ/ACQ-IA, Collect blood sample for immunological assessments Collect blood sample for pharmacogenetic analysis (should only be performed if the specific consent has been obtained) Perform oropharyngeal examination before and 60 minuttes after IMP intake⁵⁶ Instruct the subject and/or parent/caregiver on how to use the IMP First intake of IMP at the clinic. The first dose will be administered at the clinic with a minimum subsequent 60 minutes observation period⁵⁷ Dispense IMP to the subject Instruct in recording of prespecified symptomes in eDiary Activate subject and/or parent/caregiver on how to use the IMP First intake of IMP at the clinic. The first dose will be administered at the clinic with a minimum subsequent 60 minutes observation period⁵⁷ Dispense IMP to the subject Instruct in recording of prespecified symptomes in eDiary Activate subject and yro the next period Schedule date for visit 4
Visit 4 (Solicited AEs)	 Assess AEs occurring since the last visit Evaluate asthma exacerbations occurring since the last visit Assess eosinophilic oesophagitis Perform oropharyngeal examination Record changes to concomitant medication

⁵⁵ For subjects with a severe asthma exacerbation within the last 30 days prior to randomisation treatment initiation should be postponed by minimum 30 days from the time of the severe asthma exacerbation (start of OCS treatment or first day of hospitalisation). The treatment initiation can be postponed maximum 3 times, see Section 9.2

⁵⁷ For subjects with symptoms of, or in treatment for, upper respiratory tract infection, acute sinusitis, acute otitis media or other relevant infections, initiation of IMP treatment should be postponed until the condition has improved, see Section 9.2

⁵⁶ For subjects with severe oral inflammation (e.g. oral lichen planus, mouth ulcers or thrush), oral wounds or following oral surgery, including dental extraction, or following tooth loss, initiation of IMP treatment should be postponed until the oral cavity has healed, see Section 9.2

Visit ID	Procedures to be performed at the visit
	 Assess prespecified symptoms in eDiary and record solicited AEs in eCRF Check eDiary compliance Activate subject eDiary for the next period Measure height and weight. If necessary adjust Asthma Action Plan and Local and Systemic Allergic Reaction Emergency Plan Measure vital signs Measure FEV1 and calculate the % of predicted FEV1 after 6 hours of SABA washout Collect urine for pregnancy test (if applicable) Follow-up on IMP compliance Dispense asthma and rhinoconjunctivitis rescue medication as needed Dispense rescue medication for severe allergic reaction (adrenaline/epinephrine), if needed Collect used rescue medication if new rescue medication is dispensed.
TC3, 4	 Schedule date for visit 5 Assess AEs occurring since the last visit Evaluate asthma exacerbations occurring since the last visit Record changes to concomitant medication Instruct subject and/or their parent/caregiver in the use of the eDiary prior to next visit and remind them to charge the device
Visit 5	 Assess AEs occurring since the last visit Evaluate asthma exacerbations occurring since the last visit Assess eosinophilic oesophagitis Perform oropharyngeal examination Record changes to concomitant medication Measure height and weight. If necessary adjust Asthma Action Plan and Local and Systemic Allergic Reaction Emergency Plan Measure vital signs Measure FEV1 and calculate the % of predicted FEV1 after 6 hours of SABA washout Collect urine for pregnancy test (if applicable) Check eDiary compliance Activate subject eDiary for the next period Collect used IMP and rescue medication as applicable and perform drug accountability and a compliance check Dispense IMP to the subject Dispense rescue medication for severe allergic reaction (adrenaline/epinephrine auto-injector), if needed Evaluate ACQ/ACQ-IA, (subjects aged 12 years or above)

Visit ID	Procedures to be performed at the visit
	Schedule date for visit 6
TC5, 6, 7	 Assess AEs occurring since the last visit Evaluate asthma exacerbations occurring since the last visit Record changes to concomitant medication Instruct subject and/or their parent/caregiver in the use of the eDiary prior to next visit and remind them to charge the device
Visit 6	 Assess AEs occurring since the last visit Evaluate asthma exacerbations occurring since the last visit Assess eosinophilic oesophagitis Perform oropharyngeal examination Record changes to concomitant medication Measure height and weight. If necessary adjust Asthma Action Plan and Local and Systemic Allergic Reaction Emergency Plan Measure vital signs Measure FEV1 and calculate the % of predicted FEV1 after 6 hours of SABA washout Collect urine for pregnancy test (if applicable) Check eDiary compliance Activate subject eDiary for the next period Collect used IMP and rescue medication as applicable and perform drug accountability and a compliance check Dispense IMP to the subject Dispense asthma and rhinoconjunctivitis rescue medication as needed Evaluate ACQ/ACQ-IA, Schedule date for visit 7
TC8, 9, 10	 Assess AEs occurring since the last visit Evaluate asthma exacerbations occurring since the last visit Record changes to concomitant medication Instruct subject and/or their parent/caregiver in the use of the eDiary prior to next visit and remind them to charge the device
Visit 7	 Assess AEs occurring since the last visit Evaluate asthma exacerbations occurring since the last visit Assess eosinophilic oesophagitis Perform oropharyngeal examination Record changes to concomitant medication Measure height and weight. If necessary adjust Asthma Action Plan and Local and Systemic Allergic Reaction Emergency Plan Measure vital signs

Visit ID	Procedures to be performed at the visit
	 Measure FEV₁ and calculate the % of predicted FEV₁ after 6 hours of SABA washout Evaluate inhalation technique Collect urine for pregnancy test (if applicable) Check eDiary compliance Activate subject eDiary for the next period Collect used IMP and rescue medication as applicable and perform drug accountability and a compliance check Dispense IMP to the subject Dispense rescue medication for severe allergic reaction (adrenaline/epinephrine auto-injector), if needed Evaluate ACQ/ACQ-IA, (subjects aged 12 years or above) Collect blood and urine sample for safety laboratory assessments Collect blood and urine sample for biobank (should only be performed if the specific consent has been obtained) Schedule date for visit 8
TC11, 12, 13	 Assess AEs occurring since the last visit Evaluate asthma exacerbations occurring since the last visit Record changes to concomitant medication Instruct subject and/or their parent/caregiver in the use of the eDiary prior to next visit and remind them to charge the device
Visit 8	 Assess AEs occurring since the last visit Evaluate asthma exacerbations occurring since the last visit Assess eosinophilic oesophagitis Oropharyngeal examination Record changes to concomitant medication Measure height and weight. If necessary adjust Asthma Action Plan and Local and Systemic Allergic Reaction Emergency Plan Measure vital signs Measure FEV1 and calculate the % of predicted FEV1 after 6 hours of SABA washout Collect urine for pregnancy test (if applicable) Check eDiary compliance Activate subject eDiary for the next period Collect used IMP and rescue medication as applicable and perform drug accountability and a compliance check Dispense IMP to the subject Dispense asthma and rhinoconjunctivitis rescue medication as needed Dispense rescue medication for severe allergic reaction (adrenaline/epinephrine auto-injector), if needed

Confidential	Clinical Trial Protocol	
TPL45489		
Signature: OnPaper		

Visit ID	Procedures to be performed at the visit
	 Schedule date for visit 9
TC14, 15, 16	 Assess AEs occurring since the last visit Evaluate asthma exacerbations occurring since the last visit Record changes to concomitant medication Instruct subject and/or their parent/caregiver in the use of the eDiary prior to next visit and remind them to charge the device
Visit 9	 Assess AEs occurring since the last visit Evaluate asthma exacerbations occurring since the last visit Assess eosinophilic oesophagitis Perform oropharyngeal examination Record changes to concomitant medication Measure height and weight. If necessary adjust Asthma Action Plan and Local and Systemic Allergic Reaction Emergency Plan Measure vital signs Measure FEV1 and calculate the % of predicted FEV1 after 6 hours of SABA washout Collect urine for pregnancy test (if applicable) Check eDiary compliance Activate subject eDiary for the next period Collect used IMP and rescue medication as applicable and perform drug accountability and a compliance check Dispense IMP to the subject Dispense rescue medication for severe allergic reaction (adrenaline/epinephrine auto-injector), if needed Evaluate ACQ/ACQ-IA, (subjects aged 12 years or above)
TC17, 18, 19	 Assess AEs occurring since the last visit Evaluate asthma exacerbations occurring since the last visit Record changes to concomitant medication Instruct subject and/or their parent/caregiver in the use of the eDiary prior to next visit and remind them to charge the device
Visit 10 ⁵⁸	 Assess AEs occurring since the last visit Evaluate asthma exacerbations occurring since the last visit Assess eosinophilic oesophagitis

⁵⁸ Visit 10 is not applicable for subjects randomised after 31-Mar-2018 for cohort 1 and after 31-Mar-2019 for cohort 2

Visit ID	Procedures to be performed at the visit
	 Perform oropharyngeal examination Record changes to concomitant medication Measure height and weight. If necessary adjust Asthma Action Plan and Local and Systemic Allergic Reaction Emergency Plan Measure vital signs Measure FEV1 and calculate the % of predicted FEV1 after 6 hours of SABA washout Collect urine for pregnancy test (if applicable) Check eDiary compliance Activate subject eDiary for the next period Collect used IMP and rescue medication as applicable and perform drug accountability and a compliance check Dispense IMP to the subject Dispense rescue medication for severe allergic reaction (adrenaline/epinephrine auto-injector), if needed Evaluate ACQ/ACQ-IA, Schedule date for visit 11
TC20	 Assess AEs occurring since the last visit Evaluate asthma exacerbations occurring since the last visit Record changes to concomitant medication Instruct subject and/or their parent/caregiver in the use of the eDiary for the next 14 days and remind them to charge the device
